10.8.4 Reporting of Pregnancy and Lactation to the Sponsor and to Merck

Although pregnancy and lactation are not considered adverse events, it is the responsibility of investigators or their designees to report any pregnancy or lactation in a participant (spontaneously reported to them), including the pregnancy of a male participant's female partner that occurs during the trial or within 120 days of completing the trial completing the trial, or 30 days following cessation of treatment if the participant initiates new anticancer

therapy, whichever is earlier. All participants and female partners of male participants who become pregnant must be followed to the completion/termination of the pregnancy. Pregnancy outcomes of spontaneous abortion, missed abortion, benign hydatidiform mole, blighted ovum, fetal death, intrauterine death, miscarriage and stillbirth must be reported as serious events (Important Medical Events). If the pregnancy continues to term, the outcome (health of infant) must also be reported.

Such events must be reported within 24 hours to the Sponsor and within 2 working days to Merck Global Safety. (Attn: Worldwide Product Safety; [contact]).

10.8.5 Serious Adverse Events

Adverse events and adverse drug reactions are considered 'serious' if they threaten life or function.

SAEs include 'Serious Adverse Drug Reactions'. During clinical investigations, adverse events may occur, which if suspected to be medicinal product related ('adverse drug reactions') might be significant enough to lead to important changes in the way the medicinal product is developed (e.g. change in dose, population, monitoring, consent). This is particularly true for reactions, which in their most severe form threaten life or function.

Due to the significant information they provide, Serious Adverse Events (including Serious Adverse Drug Reactions) require expedited reporting. SAEs are defined as any adverse event or adverse drug reaction which:

- Results in death (i.e. fatal/grade 5 CTC AE)
- Is life-threatening (i.e. grade 4 CTC AE)
- Requires inpatient hospitalisation or prolongation of existing hospitalisation*
- Results in persistent or significant disability/incapacity; or
- Is a congenital anomaly/birth defect
- Is a new cancer (that is not a condition of the study)
- Is associated with an overdose
- Other significant medical event

Note: The term 'life-threatening' in the definition of 'serious' refers to an event in which the participant was immediately at risk of death at the time of event; it does not refer to an event, which hypothetically might have caused death if it were more severe.

*An event that results in hospitalisation or prolongs an existing hospitalisation will not be considered a serious adverse event if the only reason for the hospitalisation or prolongation was:

- Administration of chemotherapy
- Administration of trial procedures
- Placement of a permanent intravenous catheter
- Hospice placement for terminal care
- Pre-trial scheduled elective surgery
- Outpatient hospitalisation for procedures such as:
 - Elective day surgery
 - Convenience purposes (e.g. transportation difficulties)

- Planned admission as part of supportive care for insertion of PEG tube or nasogastric tube for commencement of enteral feeding (i.e. did not occur following urgent admission as a result of weight loss or other patient medical events)

Any serious adverse event, or follow up to a serious adverse event, including death due to any cause other than progression of the cancer under study that occurs to any participant from the time the consent is signed through 90 days following cessation of pembrolizumab treatment, or the initiation of new anti-cancer therapy, whichever is earlier, whether or not related to protocol treatment, must be reported within 24 hours to the Sponsor and within 2 working days to Merck Global Safety.

Additionally, any serious adverse event, considered by an investigator who is a qualified physician to be related to protocol treatment that is brought to the attention of the investigator at any time outside of the time period specified in the previous paragraph also must be reported immediately to the Sponsor and to Merck.

SAE reports and any other relevant safety information are to be forwarded to the Merck Global Safety [contact].

10.8.5.1 Serious Adverse Event Reporting

Trial Sites/Investigators

All SAEs that occur from the time a participant has signed consent for the Trial to within 90 days of the final protocol-specified treatment, intervention or procedure or the initiation of new anti-cancer therapy, whichever is earlier, are required to be reported to the Sponsor whether or not considered related to the treatment under investigation.

The **Principal Investigator (PI)** or delegate must:

- Determine whether an AE is 'Serious'
- For SAEs, the PI or delegate must then ascertain the suspected cause
- Ascertain severity
- Record the SAE in the patients' medical records and submit an SAE form.
- Report the SAE on the Trial SAE form to Sponsor and Merck no later than 24 hours after becoming aware of the event. The investigator may be requested by the Sponsor or Merck to provide or obtain specific additional follow-up information in an expedited fashion for the purpose of safety assessment

10.8.5.2 Sponsor Responsibility

The Sponsor is responsible for:

- Implementing and maintaining a suitable recording system to record information from all SAEs received from Trial Sites.
- Ensuring that the Coordinating Principal Investigator (CPI) is notified of each SAE to enable the SAE to be assessed by the CPI and any other appropriate reviewers for nature (expected/unexpected), causality and whether the TGA needs to be notified of the SAE.
- Notifying the TGA (Australia) in accordance with the regulatory authority's detailed guidance of any SUSARs that are fatal or life threatening as soon as possible but no later than 7 days after the site gained first knowledge of the event. Incomplete reports must be completed and forwarded as soon as possible within 8 additional calendar days. All

other SUSARs should be reported to the TGA within 15 days after the site gained first knowledge of the event.

- Considering information provided by (non-serious) adverse event data.
- Informing each trial site of new information arising from serious and non-serious adverse events and adverse drug reactions that may affect the conduct of the Trial, or the rights, interests, safety or wellbeing of trial patients.
- Notifying the TGA of any significant issue that has arisen from analysis of overseas reports or action that has been taken by another country’s regulatory authority within 72 hours of first knowledge.

SAEs must be reported by completing the sponsor Trial SAE form and FAXING or Emailing to the following:

Sponsor	Email: [contact]
Merck Global Safety	[contact]

SAE forms are required at the following points:

Initial Report	Within one working day/24 hours of discovery or notification of the event. If the reporting of an SAE is delayed by more than 24 hours, an explanation must be provided. This report may be signed by a clinician who is not the treating doctor.
Incomplete Reports*	If all details are not available at the time of the initial report a completed report must be sent within the next 10 days.
Updated Report	If the event is not resolved (or is ‘on-going’) at the time of the initial report, the ‘UPDATE: Outcome of Event’ section’ of the SAE Form must be completed and the form submitted to BaCT and the SAE reviewer as soon as the event is resolved (with or without sequelae) or if death has occurred.

*The Investigator is ultimately responsible for reporting the SAE and must sign the final SAE report(s). Should this Investigator not be available to sign the initial SAE form within the 24-hour period, a comment to this effect must be written on the form and the form signed by the clinician attending to the patient at the time and faxed to the Sponsor. The investigator must sign the SAE form as soon as possible and re-fax to the Sponsor

The Investigator at the Trial Site is responsible for determining the local SAE reporting requirements of the responsible HREC and subsequently notifying the HREC of SAEs as required.

All participants with serious adverse events must be followed up for outcome.

10.8.5.3 Events of Clinical Interest

Selected non-serious and serious adverse events are also known as Events of Clinical Interest (ECI) and must be recorded as such on the Adverse Event case report forms/worksheets and

reported within 24 hours to the Sponsor and within 2 working days to Merck Global Safety. (Attn: Worldwide Product Safety; [contact]).

For the time period beginning when the consent form is signed until treatment commences, any ECI, or follow up to an ECI, that occurs to any subject must be reported within 24 hours to the Sponsor and within 2 working days to Merck Global Safety if it causes the subject to be excluded from the trial, or is the result of a protocol-specified intervention, including but not limited to washout or discontinuation of usual therapy, diet, placebo treatment or a procedure.

For the time period beginning at first treatment through 90 days following cessation of treatment, or 30 days following cessation of treatment if the subject initiates new anticancer therapy, whichever is earlier, any ECI, or follow up to an ECI, whether or not related to protocol treatment, must be reported within 24 hours to the Sponsor and within 24 hours to Merck Global Safety.

Events of clinical interest for this trial include:

1. an overdose of pembrolizumab, as defined in Section 10.8.3 Definition of an Overdose for This Protocol and Reporting of Overdose to the Sponsor, that is not associated with clinical symptoms or abnormal laboratory results.
2. an elevated AST or ALT lab value that is greater than or equal to 3X the upper limit of normal and an elevated total bilirubin lab value that is greater than or equal to 2X the upper limit of normal and, at the same time, an alkaline phosphatase lab value that is less than 2X the upper limit of normal, as determined by way of protocol-specified laboratory testing or unscheduled laboratory testing.*

*Note: These criteria are based upon available regulatory guidance documents. The purpose of the criteria is to specify a threshold of abnormal hepatic tests that may require an additional evaluation for an underlying etiology.

11 STATISTICAL ANALYSIS PLAN

11.1 Statistical Analysis Plan Summary

This is a prospective, single arm Phase 1b/II study to evaluate the safety profile, efficacy and biological effects of SABR in combination with pembrolizumab in patients with oligometastatic renal cancer.

As the sample size of 30 in this study is a pragmatic one, to demonstrate a safety and efficacy signal, results are intended to be descriptive. Evidence that the combination is well tolerated, efficacious and generates activation of immune parameters will provide confidence to move to a more definitive and larger randomized study.

11.2 Statistical Analysis Plan

11.2.1 Populations for Analyses

- Enrolled participant population includes all participants who provided informed consent.
- Treated participant population (evaluative patients) is defined as the participants who completed at least one SABR treatment and received at least one dose of pembrolizumab. This is the primary population for the safety and efficacy analyses.

- Response-evaluable participants are those treated participants who have CT/MRI scans performed at respective follow-up visit.

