Whole Blood Sample ^{15,16}		X	X	X		X (9, 12 and 24 months)	X

Clinical/Administrative Assessments

- Vital signs include blood pressure, heart rate, respiratory rate and temperature. Height will be measured at screening only.
- Baseline abnormalities (using CTCAE v4.03) must be recorded from signature of informed consent to prior to start of treatment. Adverse events (using CTCAE v4.03) are then required to be assessed on day 1 of every pembrolizumab cycle and at 30 days following last pembrolizumab treatment. SABR related adverse events will be collected at every subsequent follow-up visit until 2 years after completion of SABR.

3. Conventional hypofractionated radiotherapy of **30-36Gy** may be delivered to individual lesion(s) if SABR is determined to be not technically or safely possible to deliver. If CRT is required it must be completed prior to SABR administration. **At least one lesion must receive SABR.**

4. Pembrolizumab should be administered at 5 days (+/- 3 days) of the last SABR treatment for a total of 8 cycles.

Laboratory Procedures/Assessments – All diagnostic laboratory tests should be performed within 10 days of study registration (to determine eligibility), and also within 3 days prior to every cycle of pembrolizumab (unless indicated otherwise below)

5. Urine or serum pregnancy test for patient of childbearing potential should be performed within 7 days of study registration and also 72 hours within first dose of pembrolizumab. If the urine test is positive or cannot be confirmed as negative, a serum pregnancy test will be required.

6. Haematology: Haematocrit, haemoglobin, platelet count, white blood cell count (total and differential), red blood cell count, absolute neutrophil count and absolute lymphocyte count.

7. Chemistry: Carbon dioxide (if considered standard of care only), uric acid, calcium chloride, glucose, phosphorus, potassium, sodium, magnesium, total protein.

8. Liver Function Tests: Albumin, Alkaline Phosphatase (ALP), Alanine Aminotransferase (ALT), Aspartate Aminotransferase (AST), Lactate Dehydrogenase (LDH), Gamma-Glutamyl Transferase (GGT, total bilirubin and direct bilirubin if total bilirubin is elevated above the ULN), Kidney Function Tests: Urea, creatinine.

9. Thyroid Function: T3, T4 and TSH.

10. Coagulation Profile: PT (INR), aPTT. These need only be done if there is clinical concern regarding patient anticoagulation.

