7.14 Rationale of Endpoints Definition

Primary Endpoint:

Safety (acute and long term) will be evaluated using CTCAE version 4.03 in all patients who have received at least one SABR treatment and one dose of pembrolizumab. Acute adverse events (AE) are defined as AEs occurring from the time of first SABR treatment to 30 days post

end of pembrolizumab treatment and long term AE are defined as AEs occurring after 30 days post end of pembrolizumab treatment.

Secondary Endpoints:

To evaluate effectiveness of the treatment combination, using the following measures:

- a) Overall survival (OS), time to local progression (TTLP), distant progression free survival (DPFS) and overall response rates
 - i. OS will be measured from the date of commencement of SABR treatment to the date of death from any cause.
 - ii. TTLP will be measured from date of commencement of SABR treatment to the date of first local progression. Death and commencement of a further course of systemic therapy will be considered as censoring events.
 - iii. DPFS will be measured from the date of commencement of SABR treatment to the date of first distant progression at site not documented at registration, or date of death from any cause for patients without distant progression. Commencement of second course of a further course of systemic therapy will be considered as censoring event.
- b) Overall response is defined as complete response or partial response, measured using RECIST 1.1 criteria. The RECIST definition of complete response has been modified to include disappearance of the target tumor radiographically or complete metabolic response. The primary is excluded from the evaluation of the overall response.
- c) Disease control is defined as complete response or partial response at any time after treatment commencement or stable disease for at least 6 months, measured using RECIST 1.1 criteria. The RECIST definition of complete response has been modified to include disappearance of the target tumor radiographically or complete metabolic response. The primary is excluded from the evaluation of the disease control.
- d) Pain will be evaluated using the Numerical Pain Rating Scale at the following time points: pre-conventional radiotherapy treatment (if CRT performed), pre-SABR treatment, prior to each cycle of pembrolizumab, then 3 monthly until 24 months after the end of SABR treatment.

Exploratory Endpoints

A number of translational endpoints will be evaluated including:

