8.2 Replacement of Non-Evaluable Patients

Evaluable patients are defined as participants who complete at least one SABR treatment and receive at least one dose of study drug (18-20Gy/1# to at least one lesion with at least one dose of pembrolizumab).

If a patient receives no treatment (SABR or pembrolizumab) or completes 1 x SABR treatment but does not receive any pembrolizumab treatment (i.e. withdraws or is withdrawn from the study before receiving any study drug), that patient is deemed as 'non-evaluable. Accrual will continue until 30 evaluable patients are obtained.

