11.2.3 Safety analysis

Safety will be assessed using CTCAE v4.03 and the maximum toxicity grade of each adverse event will be derived and presented in table format. The proportion of patients who suffer from grade 3 or higher toxicities (each toxicity and overall) will be provided along with its exact 95% CI for all patients who have received at least one dose of pembrolizumab and completed at least one SABR treatment. Events of clinical interest will be also tabulated (see Section 10.8.5.3 Events of Clinical Interest).

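### The grade 3+ toxicity proportion leaves out patients who start SABR but never receive pembrolizumab, and Section 11.2 assigns no analysis to them

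*Combined protocol and SAP*

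**What the plan says.** - **Analysis set.** Section 11.2.1 reads "Treated participant population (evaluative patients) is defined as the participants who completed at least one SABR treatment and received at least one dose of pembrolizumab". It also defines an Enrolled population of everyone who consented, but no analysis in Section 11.2 uses it. Of the treated set the section says: "This is the primary population for the safety and efficacy analyses".
- **Estimate.** Section 11.2.3 gives the grade 3+ proportion with an exact 95% CI. It is taken "for all patients who have received at least one dose of pembrolizumab and completed at least one SABR treatment". The same section says that "the maximum toxicity grade of each adverse event will be derived and presented in table format", without naming a population for that table.
- **Endpoint.** Section 7.14 limits the safety endpoint to patients given both treatments, then sets the acute window: "Acute adverse events (AE) are defined as AEs occurring from the time of first SABR treatment to 30 days post". Those 30 days are counted from when pembrolizumab ends.
- **Replacement.** Under Section 8.2 a patient who "completes 1 x SABR treatment but does not receive any pembrolizumab treatment" is non-evaluable, with no distinction by reason, and "Accrual will continue until 30 evaluable patients are obtained".
- **Data collection.** Adverse events are recorded from consent (Section 10.8.1). The Schedule of Events footnotes add: "SABR related adverse events will be collected at every subsequent follow-up visit until 2 years after completion of SABR". Serious events are reported from consent (Sections 10.8.5 and 10.8.5.1), and the Safety Monitoring Committee's remit includes treatment toxicity (Section 13.9).

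**The concern.** Entry to the safety set depends on something that happens after protocol treatment has begun, namely the first pembrolizumab dose. If a grade 3+ event after SABR is the reason that dose is never given, the patient leaves the set because of the outcome being measured, and a new patient fills the place. The reported proportion then describes toxicity among those who started both components. That is a fair summary of the combination. It does not show how often SABR toxicity stopped the planned sequence, which is useful to know when designing the larger randomised study that Section 11.1 has in view. The data will exist, but nothing in Section 11.2 says that they will be summarised, so showing them would be a choice made after the results are known.

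A wording point goes with this. Table 1, Section 7.14, Section 10.8.1 and the start of the late-toxicity window in Section 10.8.2 are all dated from pembrolizumab. Sections 9.5.1 and 10.3 date the safety visit from trial treatment. For a patient who never has pembrolizumab, the first group of dates is undefined.

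**Working it through.** **1. The plan's own figures.** The Clopper-Pearson 95% limits for x events in n patients are the 2.5% point of Beta(x, n − x + 1) and the 97.5% point of Beta(x + 1, n − x). With n = 30 (Section 11.2.9), all 12 rows of Table 8 reproduce after rounding. Examples are 1/30 = 3.3% (0.1–17.2), 3/30 = 10.0% (2.1–26.5) and 12/30 = 40.0% (22.7–59.4). The 22% early-stopping probability in Section 11.2.10 also reproduces: P(2 or more of 12 at 5%) = 0.1184, and 1 − (1 − 0.1184)² = 0.2227.

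**2. Adding one SABR-only patient back.**
- With a grade 3+ event the change is (x + 1)/31 − x/30 = (30 − x)/930.
- Without an event the change is x/31 − x/30 = −x/930.

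| As planned (95% CI) | One with an event added (95% CI) | Change, event | Change, no event |
|---|---|---|---|
| 0/30 = 0% (0–11.6) | 1/31 = 3.2% (0.1–16.7) | +3.2 points | 0 |
| 3/30 = 10.0% (2.1–26.5) | 4/31 = 12.9% (3.6–29.8) | +2.9 | −0.3 |
| 6/30 = 20.0% (7.7–38.6) | 7/31 = 22.6% (9.6–41.1) | +2.6 | −0.6 |
| 12/30 = 40.0% (22.7–59.4) | 13/31 = 41.9% (24.5–60.9) | +1.9 | −1.3 |

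The 0/30 row is not in Table 8; 12/30 is its last row.

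**3. How many such patients.** The documents do not say. Section 7.7.3 gives SABR grade 3 to 4 toxicity of 0% to 4% per study. If 31 patients start SABR, the upper figure gives 31 × 0.04 = 1.24 patients with such toxicity at any time. Only the share f that comes before pembrolizumab and prevents it altogether matters here. No source in the documents gives f, so it is an assumption: f = 0 gives 0 expected patients, 10% gives 0.12, 25% gives 0.31 and 100% gives 1.24. The last figure is not a strict ceiling. The cited rate leaves out grade 5 events and comes from studies with mixed doses and fractionation.

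**4. Observation time.** For a full course, all-event recording runs to about 5 + 7 × 21 + 30 = 182 days after last SABR (179 to 185 with the ±3-day start window, other visit windows ignored). For a SABR-only patient it is about 30 days if the trial-treatment anchor of Sections 9.5.1 and 10.3 applies. SABR-related events are collected to 2 years in both groups, unless a patient moves to survival-only follow-up (Section 10.4) or withdraws totally (Section 9.6).

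**The case against.** The strongest case is that the restriction is intended. The primary objective in Section 6.2 concerns SABR combined with pembrolizumab, and the same both-treatments definition appears in Sections 3, 7.14, 8.2, 11.2.1 and 11.2.3. A patient who never had pembrolizumab cannot inform combination toxicity. That stands, and it is why the evaluable set should remain primary.

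A reader might infer several stronger things that the documents do not support.
- **That Section 7.14 contradicts itself by opening the acute window at SABR.** It first limits the endpoint to patients given both treatments, and its acute window ends relative to pembrolizumab. The window is written for those patients.
- **That these events are lost or barred from reporting.** They are recorded, and reported if serious. The treated set is called primary rather than sole, and Section 11.2.11 allows deviations from the plan to be justified in the statistical report.
- **That the reported rate must be too low.** Excluded patients without an event would pull the rate down if they were counted, so the direction is not known.
- **That a delayed first dose leads to exclusion.** Section 8.2 sets no deadline. The planned gap of 2 to 8 days after last SABR is a schedule, and a patient dosed late is still counted.

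It can also be said that a count and a listing would be enough for 0 or 1 patient, and that a second proportion is a preference. The count, reasons and listing carry most of the value. The second proportion adds one column and puts the two rates side by side.

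**Conclusion.** The point holds as a minor reporting gap. The stated rule can drop a patient because of the outcome being measured, and no analysis in Section 11.2 picks that patient up. The Enrolled population contains such patients, but no analysis is assigned to it. No stated figure is wrong, and no decision threshold changes.

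One excluded patient with an event would raise the proportion by 1.9 to 3.2 points for planned results between 0/30 and 12/30. One without an event would lower it by 0 to 1.3 points. Both shifts are small beside the width of the exact intervals.

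The reading of the text is firm. Whether any case occurs is not known: 0 or 1 is a judgement based on the low cited SABR toxicity and the short planned gap before pembrolizumab.

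**What to change.** Keep the evaluable set as primary, and leave the target of 30, the 12-patient safety rule and the analysis date as they are.

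- **Section 11.2.1:** add a supplementary safety set of all participants who received any protocol SABR.
- **Section 11.2.3:** report that set's grade 3+ proportion with an exact 95% CI beside the primary one. Add the number of SABR-only patients, their reasons for not starting pembrolizumab, and a listing of their grade 3+ events. Use the adverse event data already collected.
- **Dates:** reconcile the pembrolizumab-anchored dates in Table 1 and Sections 7.14, 10.8.1 and 10.8.2 with the trial-treatment anchor in Sections 9.5.1 and 10.3, so that SABR-only patients have one reading.

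The cost is one sentence in each of the two sections, one clarifying sentence on dates, one table column and a short listing. No new data are needed. The main drawback is mixed all-event observation in the supplementary set (about 182 against about 30 days after last SABR), which needs a footnote. The supplementary rate may also look slightly less favourable.
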